## RESEARCH STRATEGY

**Scientific Premise and Overall Impact.** Young adults (YAs) with type 1 diabetes (T1D), in particular those from low-SES and racial/ethnic minority backgrounds, are widely recognized as one of the most vulnerable and difficult-to-reach populations with diabetes. In a previous mid-sized RCT, our study team obtained evidence for the efficacy of *Resilient, Empowered, Active Living (REAL)*, a community-based intervention addressing self-management and psychosocial well-being in YAs with T1D. In this study, the REAL intervention improved hemoglobin A1c ( $p=0.01$ ; clinically meaningful change of -0.81% in YAs with T1D) and diabetes-related quality of life (DQoL;  $p=0.04$ ) among low-SES, primarily minority YAs with diabetes (N=81). In a subsequent proof-of-concept study, we demonstrated that REAL is feasible and acceptable to deliver via telehealth (REAL-T), which for several reasons (see below) provides an improved method of intervention delivery for YAs with T1D. The currently proposed R01 builds upon our prior work by evaluating, on a larger scale, the efficacy, long-term effects, mediating mechanisms, and cost implications of REAL-T. *In doing so, we lay the groundwork to shift the paradigm of diabetes care through an innovative, scalable intervention which has the potential to improve health and well-being among a highly vulnerable population whose needs have not been adequately addressed by traditional self-management interventions.*

**Summary of Scientific Premise and Significance.** Diabetes exerts enormous human and economic costs, and the need for effective interventions to combat its negative effects on health and well-being is especially acute among YAs and disadvantaged populations. Further, with the cost of healthcare escalating, scalability and cost efficiency should be primary considerations in the development and adoption of innovative interventions. Therefore, this project will fill a critical gap by evaluating a telehealth-adapted self-management intervention with strong preliminary evidence demonstrating its efficacy among YAs with T1D, and which may potentially be extended to other populations including YAs with T2D and other age groups with T1D or T2D.

**Conceptual Model.** The conceptual model underlying REAL-T is outlined in Figure 1. This model was informed by a process evaluation of REAL RCT data (including statistical analysis of process variables, therapist treatment notes, and participant and therapist interviews) as well as by a review of existing literature. As suggested by the model, we expect that improvements in glycemic control (A1C, time in range) will be mediated primarily through increased performance of health behaviors (SMBG, insulin adherence), while improvements in psychosocial well-being (DQoL, depressive symptoms) will primarily be mediated by improvements in self-efficacy. Furthermore, we anticipate that changes in health behaviors will be mediated by changes in habit strength and self-efficacy. In addition to examining mediating pathways of intervention effects, we will examine whether intervention effects are moderated by key demographic or clinical variables including age, gender, ethnicity, SES, treatment regimen (multiple daily injections vs. pump; CGM yes/no), or duration of diagnosis.

**REAL-T Intervention. Overview.** The REAL-T intervention applies theoretical principles and therapeutic strategies drawn from Lifestyle Redesign, habit change theory, patient empowerment, the transtheoretical model, and motivational interviewing to address concrete self-care challenges encountered by YAs with diabetes. Lifestyle Redesign is an intervention framework which applies principles of OT to the prevention and management of chronic conditions, and has been shown to cost-effectively improve physical and mental health outcomes among diverse populations and age groups. The intervention is client-centered and individually tailored, with treatment goals and activities developed collaboratively by the client and therapist. REAL-T emphasizes the integration of self-care within sustainable habits and routines through a client-directed process of activity analysis and evidence-based strategies to promote habit formation and maintenance, including chaining, repetition, creating environmental cues, and linking activities to rewards. To meet the

[figure not shown]
needs of clients at varying stages of readiness to change, REAL-T uses communication strategies drawn from motivational interviewing to address ambivalence, and tailors treatment activities to match the client's readiness to change. This process supports the development of self-efficacy by matching activities to clients' interests, motivation, and skills, thereby facilitating experiences of mastery in diabetes self-care.

**REAL-T Intervention Process.** REAL-T participants will receive approximately 12 hours of REAL-T over 6 months, delivered by a licensed occupational therapist (OTR/L) with a minimum of 12 continuing education hours in diabetes education and 12 hours in motivational interviewing training within the past 2 years, and 20 hours of training in the REAL-T intervention manual. An endocrinologist and a psychologist will be available for as-needed consultation with the OTR/L to address emergent medical and mental health issues that fall outside of the OT scope of practice. The first intervention session takes place in-person at a location of the client's choosing (client's home, local community setting, or the OTFP outpatient clinic). If an in-person meeting is not feasible, the initial evaluation will take place via telehealth (videoconferencing). Subsequent sessions will take place using a HIPAA-compliant telehealth platform, which clients can access through both a web browser and smartphone app. Clients who do not have a computer and who are within driving distance of the study office will be loaned a study-purchased laptop for the duration of their intervention period, and clients who have a computer without a webcam will be given a webcam to facilitate videoconferencing.

**Intervention Fidelity** will be documented through three strategies that were employed successfully in our initial RCT. First, therapists will document their adherence to the intervention protocol (e.g., timing and duration of sessions, use of manualized intervention content) in all treatment notes. Second, approximately 10% of sessions, chosen at random, will be observed and/or recorded, with participants' permission, by an investigator or second intervener trained in the intervention, who will complete a fidelity checklist and provide feedback to the treating therapist. Finally, weekly meetings will be held in which the Clinical Director and treating therapists will discuss client progress and conduct refresher training.

**Communication with Providers.** For several pragmatic reasons, REAL-T will not be integrated within a particular clinic or health system, but rather will be offered to any YA meeting eligibility criteria. Thus, we will draw on several strategies to facilitate open communication with providers. First, we will request clients' medical records prior to initiating OT services, to gain an accurate overview of their medical histories and current diabetes treatment regimens. Second, we will initiate several points of informational outflow with clients' providers. These will include (a) notice of the patient's enrollment in REAL-T; (b) an initial OT evaluation and plan of care; (c) summaries of quarterly lab and psychosocial survey results; (d) notification of significant medical events; and (e) a discharge summary upon the patient's completion of REAL-T. Clients who do not have a provider at the time of enrollment will be referred by the research team to one of the study's partnering clinical sites or another provider in their area.

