**Figure 2. Participant Flow Diagram**

**Overview of Study Design.** Our primary aim is to analyze the efficacy of the 6-month REAL-T intervention in a large-scale two-arm RCT. To achieve this aim, N=210 YAs with T1D will be randomized evenly to two conditions: REAL-T or usual care control. The primary outcome is A1c, with key secondary outcomes pertaining to psychosocial well-being (depressive symptoms, diabetes distress, and DQoL). In addition, we will examine the effects of REAL-T after 3- and 6-month no-treatment follow-up periods. Furthermore, we will analyze mediating mechanisms of the intervention's effects on outcomes through structural equation modeling, and conduct exploratory analyses to evaluate the cost-effectiveness, cost impact, and change in QALYs associated with the REAL-T intervention relative to usual care. Quarterly data collection visits, performed over a 12-month period, will enable longitudinal modeling of changes in glycemic control, psychosocial well-being, and other primary and secondary endpoints. In addition, blinded CGM data collected at baseline, 6 months (immediately post-intervention), and 12 months (long-term follow-up) will facilitate a more robust analysis of the impact of the REAL-T intervention on glycemic control, through

an examination of changes in glycemic variability, percent time in range, percent time in hypoglycemia, and percent time in hyperglycemia. Figure 2 provides an overview of data collection throughout the study period.

**Participants.** Eligibility criteria, as outlined in Table 3, were chosen to ensure a medically stable pool of participants and maximize the potential of therapeutic benefit. In addition, the intervention is most appropriate for those with demonstrated diabetes care challenges and risk of developing complications, as evidenced by an elevated A1c level. Because of key differences in the pathophysiology and management of T1D and T2D, we have elected to restrict participation to YAs with T1D only.

To verify eligibility, we need to confirm A1C. Estimated A1C will be used for initial enrollment, and verified through A1C test results received from our laboratory. Estimated A1C will be identified through: (1) recent A1C from participant's medical records (directly from EMR or self-report); (2) GMI (estimated A1c) from participant's CGM software; or (3) participant self-reports that A1C has consistently been >7.5%.

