**Randomization.** Participants will be computer randomized using random block sizes. The statistician will securely maintain the randomization list on her network drive and upload to REDCap to automatically assign participants to a treatment condition after they complete baseline testing.

**Intervention.** The REAL-T intervention will be delivered as outlined above. Participants in both the REAL-T intervention and usual care control condition will continue to have access to routine diabetes care from the provider of their choosing, and their care will not be disrupted in any way due to their study participation.

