Healthcare utilization		Study-specific survey; medical record reviews	Incidence of diabetes-related outpatient medical visits, ED visits, urgent care visits, hospitalizations	Monthly				

**Data Management and Analysis.** The study's analytic plan is outlined in brief in this section; for further details, please refer to the "Statistical Design and Power" attachment in the PHS Human Subjects and Clinical Trials Information section. **Data Management:** Data will be uploaded and stored in a REDCap database management system. REDCap is a secure, web-based application designed to support data capture for research studies, providing an intuitive interface for validated data entry. It also includes audit trails for tracking data manipulation and export procedures; automated export procedures for seamless data downloads to common statistical packages; and procedures for importing data from external sources. The REDCap website is password-protected and restricted to authorized users (See Data and Safety Monitoring Plan). Research assistants will enter and reconcile all data, with further data quality checks performed by the biostatistician. Prior to conducting hypothesis tests, baseline participant characteristics will be described using frequency distributions, histograms, and summary statistics. Sparse data may be recoded to dichotomous or ordinal data.

**Power and Sample Size:** The study is powered for an intention-to-treat analysis of our primary outcome, change in A1c over the intervention period (including 3 and 6-month data). Other analyses are designated as secondary,

**Table 6. Power, given 210 participants, for testing intervention effects on A1c over 6 months (Aim 1), 9 and 12 months (Aim 2), and mediators/secondary outcomes (Aim 3).**

A1c 0-6 months (Aim 1)			A1c 0-9 or 0-12 months (Aim 2)			SEM/mediation analysis (Aim 3)		
% $\Delta$	Effect size	6-month attrition	% $\Delta$	Effect size	Annual attrition	Effect size (path a/path b)	6-month attrition	
0.81	0.55	>.99	0.81	0.55	>.99	.26/.36	.95	.95
0.59	0.40	.93	0.59	0.40	.97	.36/.26	.92	.92
0.50	0.34	.82	0.50	0.34	.89	.26/.26	.89	.88

to control the type 1 error rate in identifying statistically significant changes in the primary outcome. Power analyses were conducted using proc glmpower in SAS using a 2-sided alpha of 0.05. As described comprehensively in the "Statistical Design and Power" attachment, we calculated power for a range of

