Finally, power for analyses of mediators and secondary outcomes using structural equation modeling (SEM) is excellent for effect sizes of at least .26 for the direct effects of intervention on the mediator (path a) and of the

mediator on the outcome (path b), which are reasonable to anticipate given effect sizes derived from previous literature (see “Statistical Design and Power” for additional details).

**Aim 1: Evaluate the efficacy of REAL-T in improving glycemic control and psychosocial well-being.** Our primary analysis will evaluate efficacy for changes in A1c on an intention-to-treat basis, assessing between-group differences using mixed effects regression models. Nonparametric or other robust statistical methods will be used to evaluate the effect of deviations from normality including outliers and truncated data (e.g. eligibility criteria of >7.5% A1c) on results. An advantage to mixed effects regression models is that they incorporate all available data even when data are incomplete, providing robust effect estimates and high statistical power, as well as easy comparisons of the treatment groups. We will also conduct sensitivity analyses to evaluate whether outliers or missing data are driving the observed effects, and moderation analyses to examine whether baseline clinical or demographic characteristics (e.g., age, gender, ethnicity, SES, treatment regimen, duration of diagnosis) modify any observed effects of the intervention. **Secondary analyses:** We will evaluate the impact of the intervention on psychosocial well-being and CGM-derived measures of blood glucose control. Analysis of secondary outcomes will assess between-group differences in signed change scores on measures of % time in range (the proportion of all time measured by the CGM when blood glucose is between 70 and 180 mg/dl), % time in hypoglycemia (the proportion of time blood glucose is below 70 mg/dl), % time in hyperglycemia (the proportion of time blood glucose is above 180 mg/dl), depressive symptoms, DQoL, and diabetes distress.

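### The visible plan does not say whether clustering by therapist in the REAL-T arm is handled; a prespecified sensitivity analysis would be a cheap improvement

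*Combined protocol and SAP*

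**What the plan says.** Under Overview of Study Design, "N=210 YAs with T1D will be randomized evenly to two conditions: REAL-T or usual care control". Randomization is of individuals, so about 105 are expected per arm.

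Under REAL-T Intervention Process, the programme is about 12 hours over 6 months, "delivered by a licensed occupational therapist (OTR/L"). Under Intervention Fidelity, weekly meetings are held at which "the Clinical Director and treating therapists will discuss client progress and conduct refresher training", so there is more than one therapist. No count or caseload is given. The same two paragraphs describe a common manual with 20 hours of training, observation of about 10% of sessions, and a fidelity checklist.

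Under Intervention, participants in both arms keep their routine care, and those in the "usual care control condition will continue to have access to routine diabetes care from the provider of their choosing". No study therapist is described for controls.

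The paragraph on power gives the target of the calculation: "The study is powered for an intention-to-treat analysis of our primary outcome, change in A1c over the intervention period (including 3 and 6-month data"). It adds that "Power analyses were conducted using proc glmpower in SAS using a 2-sided alpha of 0.05". Table 6 gives "Power, given 210 participants, for testing intervention effects on A1c over 6 months (Aim 1"): effect sizes 0.55, 0.40 and 0.34 have power >.99, .93 and .82.

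Under Aim 1, the primary analysis is by intention to treat, "assessing between-group differences using mixed effects regression models". Random effects are not listed. Sensitivity analyses for outliers, missing data and non-normality are named, and so is a set of moderators. Therapist is in neither list. Data Management and Analysis describes itself as a brief outline and points to a Statistical Design and Power attachment for detail.

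**The concern.** This is a partially nested design: REAL-T participants share therapists and controls do not. The treatment is individually tailored and developed jointly by client and therapist, so some variation between therapists in effect on A1c is plausible. If it exists, A1c changes within one therapist's caseload are correlated and the REAL-T arm mean is less precise than 105 independent observations would make it. A mixed model with random effects only for repeated measures within a participant would not pick this up.

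At stake are the width of the primary confidence interval and how far the result generalizes. The opening Scientific Premise section presents REAL-T as scalable, which implies delivery by therapists other than those in the trial. On that reading, between-therapist variance belongs in the uncertainty of the estimate.

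**Working it through.** **Inputs from the documents.** N = 210, allocated 1:1 (105 per arm); two-sided alpha 0.05; stated power .93 at effect size 0.40 and .82 at 0.34. The implied SD is 0.81/0.55 ≈ 0.59/0.40 ≈ 0.50/0.34 ≈ 1.47 A1c points.

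**Assumptions, because the documents give no figure.** Number of therapists k = 3, 4, 6, 8; equal caseloads m = 105/k; therapist ICC for A1c = 0, 0.01, 0.02, 0.05; no attrition.

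**Step 1: the plan's own power.** A simple two-sample test has power Φ(d√(105/2) − 1.96). For d = 0.55, 0.40 and 0.34 this gives .979, .826 and .693, against the stated >.99, .93 and .82. A single variance factor of about 0.70 to 0.77 at 105 per arm brings the last two into line. That is plausible for a repeated-measures or baseline-adjusted calculation. The correlation and attrition inputs are not visible, so Table 6 is neither reproduced nor shown to be wrong. The power figures below rescale the stated values and so do not depend on reproducing them.

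**Step 2: actual level if therapist is left out.**
- Design effect in the REAL-T arm: DE = 1 + (m − 1) × ICC.
- True over naive variance of the arm difference: R = (DE + 1)/2.
- Actual level: 2 × [1 − Φ(1.96/√R)].

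Example, k = 4 and ICC 0.05: m = 26.25; DE = 1 + 25.25 × 0.05 = 2.26; R = 1.63; √R = 1.277; level = 2 × [1 − Φ(1.535)] = 12.5%.

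**Step 3: power if therapist is modelled.**
- Noncentrality: δ = (z_power + 1.96)/√R, with z_power = 0.915 for .82 and 1.476 for .93.
- Design effect only: Φ(δ − 1.96).
- With small-sample df: noncentral t with noncentrality δ and Satterthwaite df = (DE + 1)²/[DE²/(k − 1) + 1/104], as for an analysis of therapist means against individual controls.

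| k | ICC | √R (true/naive SE) | Actual level | df | .82 becomes: design effect only / with df | .93 becomes: design effect only / with df |
|---|---|---|---|---|---|---|
| 3 | 0.01 | 1.08 | 7.0% | 6.0 | .76 / .61 | .89 / .76 |
| 3 | 0.02 | 1.16 | 9.0% | 5.1 | .70 / .52 | .84 / .67 |
| 3 | 0.05 | 1.36 | 15.0% | 3.7 | .56 / .36 | .71 / .47 |
| 4 | 0.01 | 1.06 | 6.5% | 9.5 | .77 / .68 | .90 / .83 |
| 4 | 0.02 | 1.12 | 8.0% | 8.2 | .73 / .62 | .87 / .77 |
| 4 | 0.05 | 1.28 | 12.5% | 6.2 | .62 / .48 | .77 / .62 |
| 6 | 0.01 | 1.04 | 6.0% | 16.7 | .79 / .74 | .91 / .87 |
| 6 | 0.02 | 1.08 | 6.9% | 14.9 | .76 / .70 | .89 / .85 |
| 6 | 0.05 | 1.19 | 9.9% | 11.8 | .68 / .60 | .82 / .76 |
| 8 | 0.01 | 1.03 | 5.7% | 23.8 | .80 / .76 | .92 / .89 |
| 8 | 0.02 | 1.06 | 6.4% | 21.9 | .78 / .74 | .90 / .87 |
| 8 | 0.05 | 1.14 | 8.6% | 18.0 | .71 / .66 | .85 / .81 |

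At ICC 0, R = 1 and the level is 5.0% for any k. Unequal caseloads would raise DE at a given k and ICC.

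**Step 4: simulation check (20,000 replicates).** With 4 therapists, a test that omits therapist rejected in 4.7%, 6.5%, 8.0% and 12.7% of replicates at ICC 0, 0.01, 0.02 and 0.05, in line with the formula. Therapist means with Satterthwaite df gave 5.3%, 5.7%, 5.6% and 6.3%. With 6 therapists that analysis held about 5%. With 3 it gave 5.9% to 6.9%, so it is not exact when therapists are very few.

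**The case against.** A reader might infer that the primary model ignores therapist, that the therapists are few, that the primary test therefore has a type I error above 5%, and that Table 6 overstates power. The documents do not support these readings.

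- **Silence is not omission.** The random effects are not specified, the section calls itself an outline, and the attachment it cites is not available. The power paragraph as available also breaks off where its assumptions would be listed. The attachment may already deal with therapist.
- **The number of therapists is unknown.** The text shows more than one and nothing further.
- **Inflation is conditional.** Participants, not therapists, are randomized. If REAL-T changes A1c in nobody, therapists cannot induce correlation and the level stays at about 5%. It also does so if the conclusion concerns only the therapists used. Inflation needs therapist effects that differ yet average zero, with inference to a wider population of therapists. With the implied SD of 1.47, ICC 0.05 means a between-therapist SD of 1.47 × √0.05 ≈ 0.33 A1c points. The shared manual, training and fidelity monitoring would tend to limit such variation.
- **The remedy is costly as a primary test.** With few therapists, small-sample df remove much of the power.

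All four stand. They limit the point without removing it: the nesting in one arm is in the documents, the fidelity measures may shrink therapist variance but are not shown to remove it, and a claim of scalability reaches past the trial's own therapists.

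**Conclusion.** The point holds as a cheap improvement, not as a demonstrated error. The visible text does not state the number of therapists, their caseloads, or whether and how clustering in the REAL-T arm is handled. For inference beyond the trial's own therapists, omitting a non-zero therapist variance makes the standard error too small. Under the assumed grid, the true standard error is 1.00 times (ICC 0) to 1.36 times (3 therapists, ICC 0.05) the naive one. Every figure above 5% rests on an assumed ICC and therapist number, equal caseloads and 105 per arm. The documents cannot show where in the range this trial lies, and they do not show that the primary test is invalid or that Table 6 is wrong.

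**What to change.** 1. Record the treating therapist for each REAL-T participant, and report the number of therapists and their caseloads.
2. Keep the stated mixed model as the primary analysis.
3. Prespecify a sensitivity analysis of A1c with a therapist random effect in the REAL-T arm only, controls as singletons, and Satterthwaite or Kenward-Roger df. Report the ICC.
4. If therapists are too few to estimate the variance, report the primary result recomputed at fixed ICCs of 0, 0.01, 0.02 and 0.05. These values are conventions, not estimates from the documents.
5. State which population of therapists the conclusion covers.
6. Show Table 6 power over the same ICC range as a supplement, not as a correction.

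If the attachment already covers this, a pointer to it is enough.

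The cost is one data field, which should be easy to fill because therapists already write treatment notes, and one extra model. The downside is a wider interval in the sensitivity analysis and power that can fall sharply: from .82 to about .48 to .68 with 4 therapists at ICC 0.01 to 0.05, and to .36 with 3 at ICC 0.05. That loss is why this should be a sensitivity analysis and not the primary test.
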